One or more dosing regimens (refer to Dosing Schema Figure 1 in protocol) may be selected based on clinical findings including safety, tolerability, and PK results from previous cohorts; and after Dose Level Review Team (DLRT) review and make recommendations for the next SC cohort dose and frequency. The dose may be increased (by 1 dose level or between the dose of the previous cohort and the next higher dosing level in Figure 1 schema in protocol), kept at the same dose level or decreased by 1 or more dose levels. The dose frequency chosen (q12h, q24h, q48h,

q72h, q96h, or q7days) will be decided by the DLRT and will be based on the previous cohort PK data.

Once the SC dosing is complete, a treatment free period of 2 to not more than 3 days between stopping SC and restarting cIV will be observed. Then the cIV blinatumomab dosing will resume at 112 µg/day (weeks 5 to 6) to complete 6 weeks of treatment.

For each SC dose cohort, if ≤ 1 of the 6 DLT evaluable subjects experience a DLT during the SC administration DLT evaluation period then the dose will be determined to be tolerable and the DLRT will decide the next dose level to be initiated and the frequency of administration for the next cohort; see Section 6.2.1.2.2 in protocol for definition of the DLT evaluation period.

For each SC dose cohort, if ≥ 2 of the 6 DLT evaluable subjects experience a DLT during the SC administration then dosing will stop for individual subjects who experience a DLT, a DLRT meeting will be conducted, and further steps will be determined, such as dose de-escalation or increasing dosing interval (Figure 1 in protocol). In addition, if subjects on this cohort have not reached the SC dosing, they will be allowed to stay on study but will finish cycle 1/period 1 as cIV.

MTD will be defined as the highest dose level at which ≤ 1 of 6 subjects experience a DLT. If no subject experiences a DLT, the MTD will be defined as the maximal dose tested.

For further details, see Section 6.2.1.2.1 and Section 6.2.1.2.3 of protocol.

3.1.2 Cycle 1/Period 2

The aim of Period 2 will be to assess the MTD as derived from Period 1, or the maximum tested dose, if MTD has not been reached, for additional safety and preliminary efficacy data in an expanded cohort of up to 15 evaluable subjects receiving SC treatment only (no cIV run-in).

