If the outcome of the underlying disease is worse than that which would normally be expected for the subject, or if the investigator believes there is a causal relationship between the IP(s)/study treatment protocol required therapies and disease worsening, this must be reported as an adverse event or a serious adverse event. [Table 3](#) outlines the expected Disease-Related Events by System Organ Class (SOC).

Table 3. Disease-related Adverse Events by System Organ Class

System Organ Class (SOC)	Preferred Terms
Blood and lymphatic system disorders	Lymphadenopathy
General disorders and administration site conditions	Disease progression Fatigue
Investigations	Weight decreased
Skin and subcutaneous tissue disorder	Night sweats

Disease Related Events that would qualify as an Adverse Event or Serious Adverse Event:

- An event based on the underlying disease that is worse than expected as assessed by the investigator for the subject's condition or if the investigator believes there is a causal relationship between the investigational product(s)/study treatment/protocol-required therapies and disease worsening, this must be reported as an Adverse Event or Serious Adverse Event.

DLT Evaluable

Period 1:

To be evaluable for DLT, subjects must meet one of the following criteria:

- Cohort I and II: received treatment for or at least 8 of the 9 doses or experienced a DLT at any time while receiving blinatumomab.
- Cohort III: treated at least 4 of the 5 doses or experienced a DLT at any time while receiving the target dose of blinatumomab.

If a subject does not experience a DLT during the DLT evaluation period and does not receive all doses (q48h, q72h, q96h, or q7d dosing), at least 4 of the 5 doses (q24h dosing) or at least 8 of the 9 doses (q12h dosing) of subcutaneous Blinatumomab and taken off study for reasons other than toxicity the subject will not be considered DLT-evaluable and will be replaced as described in Protocol Section 3.4.1.

Period 2:

To be evaluable for DLT, subjects must meet one of the following criteria:

- If only cycle 1 is given : experienced a DLT during the entire duration of the SC administrations and 30 days after the last SC dose or treated with blinatumomab targeted dose for 5 days.

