- If cycle 2 is given: experienced a DLT during the entire duration of the SC administrations and 16 days following the last SC dose or until the start of cycle 2 (whichever is longer), up to 30 days after the last SC dose or treated with blinatumomab at 112 µg/day cIV for 42 days.

Dose Limiting Toxicity (DLT)

The occurrence of any of the toxicities mentioned in the section 6.2.1.2.3 of the protocol will be considered a DLT, if judged by the investigator to be related to administration of blinatumomab.

ECOG Performance Status Assessment

ECOG performance status assessment will be performed using the ECOG score. For more details please refer appendix C in Protocol.

End of Study for Individual Subject

End of IP Administration for subjects who had blinatumomab is defined as the date the decision was made to end IP as recorded on the End of IP CRF page.

End of Treatment

Defined as the last assessment for the protocol-specified treatment phase of the study for an individual subject.

End of Follow-up

Defined as the date that the last subject completes the last protocol-specified assessment in the study.

Enrollment Date

Enrollment Date is defined as the date of enrollment collected on the CRF.

Subject Level End of Study (EOS) Date

End of study for each subject is defined as the date the subject last completed a protocol-specified procedure. The date will be recorded on the End of Study CRF page.

Investigational Product

The term 'investigational product' is used in reference to blinatumomab.

Last Dose Date of Investigational Product

This is the stop date of the last dose of blinatumomab administration reported on the Investigational Product Administration CRF.

Maximum Tolerated Dose (MTD)

MTD will be defined as the highest dose level at which ≤ 1 of 6 subjects experience a DLT. If no subject experiences a DLT, the MTD will be defined as the maximal dose tested.

Optional Cycle 2

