A subject may receive a second cycle of blinatumomab administered SC if the subject derived clinical benefit (demonstrated on staging scans) from Cycle 1/Period 2 treatment. If no clinical benefit occurred with SC in Cycle 1/Period 2 then an optional Cycle 2/Period 2 may still be given but will administered as a cIV infusion instead of SC. If blinatumomab is administered as a cIV infusion it will be dosed at 9 $\mu\text{g/day}$ cIV for 7 days for days 1 through day 7, next the dose will be escalated (dose step) to 28 $\mu\text{g/day}$ cIV for 7 days starting on day 8 through day 14, and then advanced to 112 $\mu\text{g/day}$ cIV for 28 days starting on day 15 through day 42.

Percent Change From Baseline

Percent change from Baseline is the arithmetic difference between post-Baseline and Baseline divided by Baseline values times 100.

Screened

A subject is considered in screening once a consent form has been signed.

Study Day 1

Study day 1 is defined as the first day of administration of the investigational product after enrollment. The day prior to Study Day 1 is considered Day -1.

Study Day

Post study day 1: study day= (date - date of Study Day 1) + 1

Pre study day 1: study day= (date – date of Study Day 1)

Study Duration

For an individual subject, the length of participation includes a 14 day screening period, up to a 14 week treatment period (6 weeks for cycle 1 in Period 1 and Period 2 and 6 weeks for the optional Cycle 2, separated by a 14 day treatment free interval), and a safety follow-up visit (30 days [+ 7 days] after the last dose of study treatment).

For subjects who complete the protocol from the date of first dose through optional Cycle 2, the entire duration of the study will take approximately 20 weeks to complete. However, individual study duration will vary depending on administration of a second cycle and tolerability of blinatumomab by an individual subject.

Treatment emergent adverse events (TEAEs)

A treatment emergent adverse event refers to the adverse event that starts on or after first dose of blinatumomab through 30 days after the last dose of blinatumomab. It is indicated by the flag whether an event start before first dose of blinatumomab on the Event CRF page. This reporting window also applies to treatment-emergent serious adverse events (SAEs).

7. Analysis Subsets

The analysis of all endpoints, unless noted otherwise, will be conducted on the Full Analysis Set defined in [Section 7.1](#).

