7.3 DLT Analysis Set

All subjects who are DLT-evaluable are included in this analysis set as defined in [section 8.1.1.2](#)

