8.1.1.2 Dose Limiting Toxicity Rules

Cycle 1/Period 1

The DLT evaluation period includes the entire week 4 (7 days) which is the week that blinatumomab is administered SC during Cycle 1/Period 1 of the study. To be evaluable subjects need to fulfill the criteria described in [section 6](#).

If ≤ 1 of the 6 evaluable subjects in a dose SC cohort experience a DLT during the SC administration, then the dose will be determined to be tolerable and the next dose-cohort level will be initiated in a new dose-cohort of subjects after review by the DLRT.

If ≥ 2 subjects of the 6 evaluable subjects in a SC dose cohort experience a DLT during SC administration then dosing will stop for individual subjects who experience a DLT, a DLRT meeting will be conducted, and further steps will be determined.

Additionally, the DLRT will meet:

- once dose-cohort 1 has completed subcutaneous dosing
- once dose-cohorts 2 and 3 have completed subcutaneous dosing
- once any additional cohorts complete dosing if additional dose-cohorts are tested to determine the MTD in Cycle 1/Period 1

Cycle 1/Period 2

For subjects who receive optional Cycle 2 (cIV dosing period) after Cycle 1/Period 2 (SC dosing period), the DLT evaluation period includes the entire duration of SC administration in Cycle 1 and 16 days following the last SC dose (56 days in total) or until the start of optional Cycle 2, whichever is longer, up to 30 days after the last SC dose of Cycle 1. For subjects who do not receive optional Cycle 2, the DLT evaluation period includes the entire duration of SC administration and 30 days following the last SC dose (70 days in total). Continuous monitoring for early termination of the trial will be performed by DLRT (refer to [Section 3.1.3](#) and [Section 8.1.1](#)).

9. Data Screening and Acceptance

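### SAP Section 6 makes DLT-free Period 2 subjects who take Cycle 2 evaluable only after 42 days of cIV at 112 µg/day, which no planned Period 2 schedule provides

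*SAP*

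**What the plan says.** SAP Section 6 (Definitions, DLT Evaluable, Period 2) gives two alternatives, depending on whether Cycle 2 is given.

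- **Cycle 1 only:** a DLT during SC dosing or the 30 days after it, "or treated with blinatumomab targeted dose for 5 days".
- **Cycle 2 given:** a DLT during SC dosing and the following 16 days or until Cycle 2 starts, whichever is longer, "up to 30 days after the last SC dose or treated with blinatumomab at 112" µg/day "cIV for 42 days".

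The planned treatment is set out nearby. SAP 3.1.2 describes Period 2 subjects in Cycle 1 as "receiving SC treatment only (no cIV run-in"). The Optional Cycle 2 entry in SAP Section 6 offers two routes. The first is SC: "A subject may receive a second cycle of blinatumomab administered SC if the subject derived clinical benefit". The second, without clinical benefit, is cIV: 7 days at 9 µg/day, 7 days at 28 µg/day, then 112 µg/day "cIV for 28 days starting on day 15 through day 42".

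SAP 7.3 defines the DLT Analysis Set: "All subjects who are DLT-evaluable are included in this analysis set as defined in" Section 8.1.1.2. That section sends the reader on to Section 6 ("To be evaluable subjects need to fulfill the criteria described in" Section 6), but only under its Cycle 1/Period 1 heading. Its Period 2 paragraph gives an evaluation window and no evaluability criterion. Section 6 is therefore the only Period 2 evaluability definition in the SAP.

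Protocol 6.2.1.2.2 gives the Period 2 window and sets no Cycle 2 exposure condition. Protocol 3.4.2 bases Period 2 replacement on Cycle 1: at least 85% of the first 8 planned SC doses.

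**The concern.** The Period 2 DLT window belongs to Cycle 1 SC treatment. Whether a subject can be assessed for toxicity in that window should depend on Cycle 1 exposure and follow-up. The SAP instead makes it depend on what the subject receives in Cycle 2, and names an amount that the Cycle 2 schedule does not contain.

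The two limbs also act in opposite directions. A subject with a DLT is always kept. A DLT-free subject who goes on to Cycle 2 must pass the exposure test and cannot fall back on the 5-day limb, which applies only when Cycle 1 alone is given. Membership of the set is then selected on the outcome it is meant to measure. On the lenient reading it is also selected on clinical benefit, because that decides who receives SC Cycle 2.

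DLT incidence is part of the primary endpoint (SAP 4.1.1), which is not limited to Period 1, and protocol 10.1.2 restricts DLT analysis to evaluable subjects.

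**Working it through.** **1. Days available against days required**

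Required by SAP Section 6: 42 days at 112 µg/day cIV. Planned in Period 2 (SAP 3.1.2 and Section 6, Optional Cycle 2):

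| Route | cIV days at 9 / 28 / 112 µg/day | Total cIV days | Shortfall at 112 |
|---|---|---|---|
| Cycle 1/Period 2 (SC) | 0 / 0 / 0 | 0 | – |
| Cycle 2 by cIV | 7 / 7 / 28 (days 15–42: 42 − 15 + 1 = 28) | 42 | 42 − 28 = 14 |
| Cycle 2 by SC | 0 / 0 / 0 | 0 | 42 |

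- *Literal reading (42 days at 112 µg/day):* the most a Period 2 subject can accumulate is 0 + 28 = 28. No planned Period 2 route qualifies.
- *Lenient reading (42 days of stepped cIV):* 7 + 7 + 28 = 42, so a subject who completes cIV Cycle 2 qualifies. SC Cycle 2 gives 0 of 42.

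**2. Timing against the DLT window**

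Count Cycle 1 as 42 days, followed by the 14-day treatment-free interval of protocol 6.2.1.1.3.

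- Cycle 2 day 1 = 42 + 14 + 1 = study day 57. Cycle 2 day 42 = day 98.
- The last Cycle 1 SC dose in protocol Table 6 falls on day 42 (q48h, q72h) or day 40 (q96h, q7d).
- Adding 16 days, the window closes on day 58 or day 56.
- Even the lenient limb is met 98 − 58 = 40 to 98 − 56 = 42 days after the window has closed.
- Literally, 42 days at 112 µg/day counted from Cycle 2 day 15 would end on Cycle 2 day 15 + 41 = 56, which is 14 days past the planned end.

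**3. What the selection could do to a Period 2 rate**

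The SAP plans no such rate, so this is an illustration. Assumptions: 15 subjects, 3 with a DLT, and Cycle 2 uptake as shown. Intervals are Clopper-Pearson 95%. With all 15 subjects the rate is 3/15 = 20.0% (4.3–48.1).

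*Literal reading; all DLT-free Cycle 2 takers drop out:*

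| DLT-free Cycle 2 takers | Rate |
|---|---|
| 3 | 3/12 = 25.0% (5.5–57.2) |
| 6 | 3/9 = 33.3% (7.5–70.1) |
| 9 | 3/6 = 50.0% (11.8–88.2) |

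*Lenient reading; 6 DLT-free Cycle 2 takers, of whom the cIV takers all complete:*

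| Number of the 6 on SC | Rate |
|---|---|
| 0 | 3/15 = 20.0% (4.3–48.1) |
| 2 | 3/13 = 23.1% (5.0–53.8) |
| 4 | 3/11 = 27.3% (6.0–61.0) |
| 6 | 3/9 = 33.3% (7.5–70.1) |

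With no DLTs the estimate stays at 0%. Only the upper limit moves: 21.8% for n = 15, 24.7% for n = 13, 33.6% for n = 9.

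**4. The neighbouring figures are sound**

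The Beta(0.5, 1.5) prior with the 80% posterior rule reproduces SAP Table 1: boundaries 3 (n = 5–6), 4 (7–10), 5 (11–13) and 6 (14). Exact recursion gives early-stopping probabilities of 17.4, 30.3, 44.9, 72.4, 90.2 and 97.8%, and mean sample sizes of 13.7, 12.7, 11.6, 9.3, 7.3 and 6.1, which match SAP Table 2. The error found here lies in the evaluability definition, not in the monitoring design.

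**The case against.** The strongest reply is that no planned result changes. SAP 10.5.1.1 and protocol 10.4.1 plan DLT summaries for Period 1 only. The MTD is a Period 1 quantity, the stopping rule in SAP 3.1.3 is stated for subjects treated, and Period 2 toxicities enter the adverse event tables through the Full Analysis Set whatever the DLT flag says. All of this stands and limits the severity. The planned output that is affected is the analysis-subset listing and summary in SAP 10.2.

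A second reply is that SAP 7.3 points to 8.1.1.2, whose Period 2 paragraph has no 42-day condition, and that SAP Section 11 declares no change from the protocol. One could therefore argue that the Section 6 condition never reaches the set. But 8.1.1.2 then supplies no Period 2 evaluability rule at all. Whoever derives the flag must either apply Section 6 or make an undocumented choice.

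Third, the illustration rests on assumed counts and the intervals overlap widely. That is correct. It shows the direction and possible size of the bias, not a forecast.

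Fourth, the window dates hold only for an on-schedule Cycle 2. A later start can extend the window to 30 days after the last SC dose (day 70 or 72). The exposure condition would still be met only after the window closes, because Cycle 2 itself runs 42 days from that later start.

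Finally, choosing a minimum Cycle 1 exposure may need a protocol clarification, since protocol 6.2.1.2.2 states none for Period 2. That is a fair point about cost.

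**Conclusion.** The concern holds. Read literally, the Cycle 2 limb cannot be met by any planned Period 2 schedule (28 or 0 days against 42). On the lenient reading it still excludes every DLT-free subject who takes Cycle 2 by SC. Both conclusions follow from the SAP's own schedule and need no assumption.

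If the Section 6 rule is applied, Period 2 membership of the DLT Analysis Set depends on the outcome. A DLT rate computed on it is too high whenever at least one DLT occurs and at least one DLT-free subject is dropped. In the assumed examples, 20.0% rises to between 23.1% and 50.0%.

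This should be fixed before database lock, but it does not undermine the trial. The Period 1 DLT summary, the MTD and the Period 2 stopping boundaries are not shown to be affected.

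**What to change.** - **SAP Section 6.** Remove the 42-day cIV condition from the Period 2 definition. Define evaluability on Cycle 1 only, identically for subjects with and without Cycle 2: either a DLT in the protocol 6.2.1.2.2 window, or a stated minimum Cycle 1 SC exposure. Reconcile the 5-day criterion with protocol 3.4.2, where 85% of 8 doses is 6.8, that is at least 7 doses.
- **SAP 7.3.** Point directly to this definition.
- **SAP 10.5.1.1.** Add a Period 2 DLT listing and incidence summary on the corrected set, because the primary endpoint is not confined to Period 1.
- **SAP 8.1.1.2.** Reconcile the label that treats Cycle 2 as a cIV period with the SC option in Section 6.
- **Minor wording, SAP Section 6, Cohorts I and II.** Align the phrase allowing a DLT at any time on blinatumomab with the week 4 window, which the DLT definition in protocol 6.2.1.2.3 already imposes.

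The cost is SAP wording, one listing and one table from data already collected, and possibly a short protocol clarification of the minimum Cycle 1 exposure for Period 2. Nothing changes in dosing or conduct.

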7.1 Full Analysis Set

All subjects who receive blinatumomab are included in the full analysis set (FAS). This definition is in line with the intent-to-treat (ITT) principle in single-arm open-label studies. For the dose escalation part of the study subjects will be analyzed according to the initial blinatumomab dose received. For the dose expansion, subjects will be analyzed according to the dose selected for this part of the study.

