#### 10.1.2 Analysis Sets

The statistical analysis will be based on the following study populations. Subjects will be summarized separately by the planned dose cohorts.

The analysis of all endpoints, unless noted otherwise, will be conducted on the Full Analysis Set.

The analysis of DLTs will be restricted to DLT-evaluable subjects.

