## 10.4 Planned Methods of Analysis

### 10.4.1 General Considerations

A clinical study report will be generated for the final analysis. All documented parameters will be adequately evaluated. The data will be summarized overall, and by assigned dose cohort using suitable descriptive measures. Individual data will be listed.

The DLT findings during Period 1 will be tabulated.

Descriptive statistics for demographic, safety, PK parameters, and biomarker data will be summarized by dose, dose schedule, and time as appropriate. The PK parameters will be estimated with non-compartmental analysis. For categorical variables, the number and percentage of subjects in each category will be summarized. Continuous variables will be summarized by n, mean, standard deviation, median, Q1 (25th percentile), Q3 (75th percentile), minimum, and maximum values.

Point estimates for efficacy endpoint incidences will be accompanied by 2-sided 95% exact binomial confidence intervals (CIs) ([Clopper CJ, Pearson ES, 1934](#)).

When data are summarized by time, the values recorded against the scheduled time points listed in the protocol will be used. When assessing minimum/maximum increases or decrease over the study, all assessments including unscheduled assessments will be used. In general, data listings will be sorted by dose, subject, and time.

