3.1 Study Design

This is a global multi-center, Phase 1b open-label study investigating the safety and PK of blinatumomab administered subcutaneously for the treatment of relapsed/refractory indolent NHL. The SC administration of blinatumomab will be tested for the first time in humans.

Period 1 of the study will focus on the determination of PK, bioavailability, and safety profile of blinatumomab SC administration. The PK and bioavailability data from Period 1 of the study will be used in conjunction with safety data (DLT) to determine the SC

MTD. The MTD or the maximum tested dose, if MTD is not reached, will be further tested in Period 2 in an expanded cohort. Efficacy of blinatumomab administered subcutaneously will also be investigated in each period of the study.

3.1.1 Cycle 1/Period 1

In Period 1, 3 or more separate dose cohorts of up to 6 DLT evaluable subjects each will be enrolled and undergo treatment as follows:

- Subjects will undergo an initial cIV blinatumomab run-in period (weeks 1 to 3) followed by a 12-hour treatment free period.
- Subjects will then receive SC administration (week 4) followed by a treatment free period of 2 to not more than 3 days.
- After the SC administration period, subjects should return to receive cIV treatment to complete 6 weeks of therapy (weeks 5 to 6).

For all cohorts, the initial cIV dose of blinatumomab will be 9 µg/day for the first 7 days (to mitigate for potential cytokine release syndrome [CRS] and neurologic events associated with introduction to blinatumomab) which then will be escalated (dose-step) to 28 µg/day starting on day 8 through day 14 (week 2), and to 112 µg/day starting on day 15 until day 21 (week 3).

After stopping cIV blinatumomab, there is a 12-hour treatment free period before starting SC blinatumomab. SC blinatumomab starts after the 12-hour treatment free period and will be administered (week 4) as the following dose-cohort levels:

- Dose Cohort 1: 112 µg q12h × 5 days for a total of 9 doses (n= 6)
- Dose Cohort 2: 225 µg q12h × 5 days for a total of 9 doses (n = 6)

(Note: A total of 9 SC doses will be given for the q12h dosing, so intensive PK samples can be obtained on day shift to reduce errors).

- Dose Cohort 3: 450 µg q24h × 5 days for a total of 5 doses (n = 6)
- Additional Dose Cohorts: Dose level and dosing frequency to be determined as described below

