7.2 Safety Analysis Set

For each part of the study, the safety analysis set will be the same as the FAS. All other analysis sets will be a subset of FAS.

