10.1 General Principles

Descriptive statistics will be provided for selected demographics, safety, immunogenicity, PK, PD, and biomarker data. Descriptive statistics on continuous measurements will include means, medians, standard deviations, and ranges, while categorical data will be summarized using frequency counts and percentages. Data will be summarized by dose cohort and by time as appropriate. Graphical summaries of the data may also be presented. When data are summarized by time, the scheduled time points listed in the protocol will be used). For statistical analyses comparing change from baseline, only subjects with both baseline and at least one post-baseline assessment will be included. When assessing minimum/maximum increases or decreases over the study, all assessments, including unscheduled assessments will be used.

The final analysis will be triggered when target enrolment is complete, and all subjects complete the study or withdraw from the study. The data will be analyzed once they have been entered, cleaned, and locked.

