10.5 Safety Analyses

Unless otherwise specified, statistical analyses on safety endpoints will be done using subjects from the full analysis set, which includes subjects that are enrolled and received at least 1 dose of blinatumomab.

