10.5.1 Adverse Events

The Medical Dictionary for Regulatory Activities (MedDRA) version 19.0 or later will be used to code all adverse events to a system organ class and a preferred term.

The severity of each adverse event will be graded using CTCAE version 4.0 criteria. Subject incidence of treatment emergent events and treatment related treatment emergent events will further be summarized by worst severity grade.

Subject incidence of all treatment emergent, serious treatment emergent, treatment related, serious treatment related, those leading to withdrawal of investigational product or other protocol-required therapies, and fatal adverse events will further be tabulated by system organ class and preferred term for each dose cohort in descending order of frequency. The above adverse event tables will include disease related events and will not be created if two or fewer subjects in the study experience the adverse event. Similar summaries will be repeated for EOIs. Time to onset and duration of selected EOIs (infection and neurologic events) may also be summarized.

Subject incidence of disease related events and fatal disease related events will be tabulated by system organ class and preferred term for each dose cohort. All DREs and fatal DREs would be tabulated by system organ class and preferred term separately.

DREs should be included with AEs in any submission datasets, integrated summaries and in CTD reporting.

Tables with AEs as above will be produced for period 1 for SC and cIV dosing separately. Listings of any on-study deaths, including early withdrawals due to adverse events will be provided should they occur.

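### SAP 7.1 groups Period 1 by initial dose, which is the same for everyone, and the Period 1 SC adverse event tables default to an any-route denominator with no SC onset window

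*SAP*

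**What the plan says.** **Grouping.** SAP 7.1: "For the dose escalation part of the study subjects will be analyzed according to the initial blinatumomab dose received". SAP 3.1.1: "For all cohorts, the initial cIV dose of blinatumomab will be 9" µg/day. Elsewhere the unit is the dose cohort. Protocol 10.1.2: "Subjects will be summarized separately by the planned dose cohorts". Protocol 10.4.1: "The data will be summarized overall, and by assigned dose cohort using suitable descriptive measures". SAP 10.1: "Data will be summarized by dose cohort and by time as appropriate". SAP 10.5.1 also specifies its adverse event tables for each dose cohort. SAP 11 declares no departure from the protocol.

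**Denominator.** SAP 10.5.1: "Tables with AEs as above will be produced for period 1 for SC and cIV dosing separately". It names no population for these tables, so the general rules apply. SAP 7.2: "For each part of the study, the safety analysis set will be the same as the FAS". SAP 10.5 uses the FAS unless told otherwise, "which includes subjects that are enrolled and received at least 1 dose of blinatumomab". Route plays no part in membership.

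**Onset window.** SAP 6 defines treatment-emergent events by a single window, from the first blinatumomab dose to 30 days after the last, whatever the route. SAP 8.1.1.2 sets a 7-day week 4 window, but for DLTs only.

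**The concern.** The primary objective is the safety of SC blinatumomab, and adverse event incidence is part of the primary endpoint. In Period 1 each subject has cIV before and after a short SC phase, so a table of SC adverse events needs three things: a grouping that separates the SC regimens, a denominator of people exposed to SC, and a rule for which events count as SC events. The first is stated in a form that cannot work. The second falls to a default that includes unexposed subjects. The third is not stated.

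The FAS can hold Period 1 subjects with no SC exposure for two reasons. Some leave during the cIV run-in and are replaced (protocol 3.3 and 3.4.1). Others had not reached SC when two or more subjects in their cohort had a DLT, and they finish the cycle on cIV (SAP 3.1.1; protocol 6.2.1.4.2, after Table 2). Counting them in an SC table lowers the SC rates. A loose onset rule could instead move cIV events into the SC table and raise them. In an open-label study these choices should be fixed before the tables are produced.

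**Working it through.** **1. Grouping.** Initial dose received, all Period 1 cohorts: 9 µg/day cIV. Distinct values: 1, so SAP 7.1 gives 1 group. With about 30 evaluable subjects and 6 per cohort, 30 / 6 = 5 cohorts. The two rules cannot both be followed.

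Reading the sentence as the initial SC dose does not repair it. Some FAS members never receive SC, and the dose review team may keep a dose and change its frequency (SAP 3.1.1), so dose alone could merge two regimens.

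**2. Size of the Period 1 FAS.** Inputs from protocol 3.3 and SAP 3.2: 30 evaluable in Period 1, up to 15 in Period 2, about 20% early discontinuation, about 54 enrolled.

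- Reproducing the plan's figure: (30 + 15) × 1.2 = 54.
- Same inflation for Period 1: 30 × 1.2 = 36, so about 6 replaced subjects.

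**3. Dilution under the FAS default.** Shown rate = true SC rate × (SC-treated / FAS). The documents do not say how many replaced subjects will have received SC, so the range is:

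| Replaced subjects who never received SC | SC-treated / FAS | True 30% shows as | True 50% shows as |
|---|---|---|---|
| All 6 | 30/36 = 0.833 | 25.0% | 41.7% |
| Half (3) | 33/36 = 0.917 | 27.5% | 45.8% |
| None | 36/36 = 1 | 30% | 50% |

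The first row matches protocol 3.3, which places the expected Period 1 loss in the cIV run-in. The last row is possible because protocol 3.4.1 also allows replacement for missed SC doses or PK samples. If instead 20% of those enrolled were lost, 30 / 0.8 = 37.5, or 38 enrolled. The worst case would then be 30/38 = 0.789, showing 30% as 23.7% and 50% as 39.5%.

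**4. Onset window.** On the nominal schedule, cIV runs on days 1 to 21, the SC phase on days 22 to 28 (28 − 22 + 1 = 7 days), and cIV again on days 29 to 42. The treatment-emergent window for a subject with one cycle is 42 + 30 = 72 days and covers all of this. The relatedness question in protocol 9.2.2.1 asks about the product, not the route, so onset date is the only basis for assignment.

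**5. Partial onset dates.** SAP Appendix A can set a partial or missing start date to the date of first dose, which in Period 1 is a cIV day. An event from the SC week could leave the SC table in this way.

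**The case against.** **Denominator.** A reader might infer that the SC tables have no stated denominator. The documents do not support that: SAP 7 and 10.5 supply the FAS by default, and on this point the tables can be programmed. The criticism is that the default is the wrong population for an SC-specific rate.

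**Grouping.** The table-level instructions use dose cohort, and one 9 µg/day group would defeat them, so a programmer would probably set SAP 7.1 aside. That limits the practical harm. It does not remove an undeclared contradiction in the definition of the main analysis set.

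**Window.** Protocol Table 3 labels week 4 as SC administration and day 29 onward as cIV, which points to the sensible window. But no text applies it to adverse events. A reader might also infer that the SC window could run to 30 days after the last SC dose, or take the SC week's small share of the treatment-emergent window as a measure of bias. Nothing in the documents proposes either for Period 1.

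**Stopped cohorts.** A reader might infer severe dilution, such as 2 SC-treated subjects of 6, in a cohort halted after two DLTs. This needs DLTs in both of the first two SC subjects, with all six started at the minimum 96-hour spacing and no bridging days. Two DLTs in two subjects has probability 0.3² = 9% at a 30% DLT rate and 0.1² = 1% at 10%. Several grade 3 events also become DLTs only if unresolved after 7 days. It is not a fair gauge of the effect.

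**Consequences.** No hypothesis is tested, individual data are listed, and the dose review team works from listings. Subjects are in hospital during SC dosing, so partial onset dates in that week should be few. All of this stands and keeps the point to reporting.

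**Conclusion.** The point holds in three parts. SAP 7.1 is wrong as written: it yields one Period 1 group where the protocol and the rest of the SAP require cohorts. The FAS default puts subjects without SC exposure into the SC adverse event denominator. No rule assigns Period 1 events to a route.

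The dilution runs from none to a factor of 30/36 (30% shown as 25%, 50% as about 42%). The upper end assumes the plan's own 20% inflation, losses entirely in the cIV run-in as protocol 3.3 anticipates, and all 30 evaluable subjects SC-treated. A reader might infer that the plan therefore understates SC toxicity overall. That does not follow: an onset rule that is too wide would push the rates up, and the plan fixes no net direction.

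DLT incidence has its own analysis set. The escalation and MTD rule, PK, and exposure by route are likewise unaffected.

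**What to change.** - Replace the SAP 7.1 sentence with: *Period 1 subjects are analysed by assigned SC dose cohort (dose and frequency).*
- Use FAS subjects with at least one SC dose as the denominator for the Period 1 SC adverse event tables. Keep the FAS for cIV and whole-study tables.
- Assign an event to SC if its onset falls from the first SC dose, or from any resumed SC dose, until cIV restarts.
- For subjects who do not restart cIV, close the SC window at the end of the week 4 SC period. Show later events, up to 30 days after the last dose, separately. Running the SC window on to the end of the treatment-emergent period would give these subjects about 30 extra days at risk.
- Assign partial onset dates that could fall in the SC phase to SC, not to the first (cIV) dose.

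The cost is SAP wording and programming. Dosing dates and event onset dates are already collected (protocol 6.2.1.1 and 9.2.2.1). SC rates may look somewhat less favourable.
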